3 OBJECTIVES

3.1 Primary Objective:

PREVENT V.5.0

• To assess the local and systemic safety of intranasal Q-GRFT after 14 doses

3.2 **Primary Endpoint:**

• The proportion of participants who experience a related Grade 2 or higher adverse event

3.3 Secondary Objectives:

- Persistence: To determine the persistence of Q-GRFT in the respiratory tract after a single dose and after 13 days of daily use as assessed by nasopharyngeal swab
- Pharmacokinetics: To determine the systemic absorption of Q-GRFT after administration of a single dose and after 13 days of daily use
- Acceptability: To assess the acceptability of a Q-GRFT nasal spray

3.4 Secondary Endpoints:

- Persistence: Q-GRFT concentrations from nasopharyngeal swabs collected 24 hours after a single dose and 24 hours after 13 consecutive daily doses
- Pharmacokinetics: Q-GRFT concentrations in plasma 24 hours after the first dose and 24 hours after the 13th consecutive daily dose
- Acceptability: Self-reported assessment of qualities of the experience with the nasal spray through a Likert scoring of acceptability questions

3.5 Exploratory Objectives:

- To assess the impact of Q-GRFT nasal spray on smell
- Persistence: Q-GRFT concentrations from oropharyngeal and nares swabs collected 24 hours after a single dose and 24 hours after 13 consecutive daily doses
- Presence of Q-GRFT in the gastrointestinal tract after 13 days of consecutive use
- Determine the potential of the Q-GRFT study drug product to induce an immune response by measuring the generation of anti-drug antibodies (ADAs) in plasma/blood samples after multiple Q-GRFT intranasal spray treatments

3.6 Exploratory Endpoints:

- Change in Brief Smell Identification Test (BSIT) score after 13 days of consecutive daily doses compared to baseline
- Persistence: Q-GRFT concentrations from oropharyngeal and nares swabs collected 24 hours after first dose and 24 hours after the 13th consecutive daily dose
- Presence: Q-GRFT concentrations from rectal swab collected 24 hours after the 13th consecutive daily dose
- Immunogenicity of Q-GRFT study product delivered by an intranasal spray system
- Humoral antibody responses to Q-GRFT in plasma/blood by ELISA

4 STUDY DESIGN

4.1 Identification of Study Design

This is a phase I randomized, placebo-controlled, single site safety study

4.2 Summary of Major Endpoints

The proportion of participants who experience a related Grade 2 or higher adverse event.

4.3 Description of Study Population

The study population will be people who meet criteria outlined in Section 5.

4.4 Time to Complete Accrual

Accrual is expected to be completed in approximately 6 months.

4.5 Study Groups

Participants will be randomized 2:1 to Q-GRFT or placebo intranasal spray.

4.6 Expected Duration of Participation

The duration of study participation is expected to be approximately 6-8 weeks. This includes the screening period.

4.7 Site

There is a single study site: UPMC Magee-Womens Hospital, Pittsburgh, PA.

5 STUDY POPULATION

5.1 Selection of the Study Population

The inclusion and exclusion criteria will be utilized to ensure the appropriate selection of study participants.

5.2 Recruitment

Participants will be recruited using a combination of outreach for instance through research registries at the University of Pittsburgh, use of IRB approved informational flyers and posters, and through outreach in the areas and clinics of UPMC Magee-Womens Hospital. This combination of recruitment strategies has proven to successfully provide an adequate number of eligible participants for a wide range of studies evaluating investigational products. The study team includes research staff members who can provide potential study participants with a concise synopsis of the study objectives and rationale. If potential participants contact the study office by telephone, text or email, the study staff will review the study objectives and review the inclusion and exclusion criteria with the potential participants utilizing an IRB approved script.

5.3 Retention

Retention of study participants is a high priority and retention of participants in other phase 1 studies of investigational products has been high (>95%) within our research group. This is accomplished through the development of strong locator information including alternative contacts including friends and family members, telephone reminders prior to study visits and the development of rapport with participants.

5.4 Inclusion Criteria

Participants must meet all the following criteria to be eligible for inclusion in the study:

- 1) Age 18-55
- 2) Willing and able to provide written informed consent
- 3) In general good health as determined by the site clinician
- 4) Willing to have SARS-CoV-2 test performed at screening Note regarding positive SARS-CoV-2 test result at screening visit:
 Positive result and asymptomatic: participants may enroll 14 days after a positive test result if they remain asymptomatic
 Positive test result and is/becomes symptomatic: participants may enroll 14 days after the start of

symptoms or positive results (whichever occurred later) as long as afebrile for 24 hours

- 5) Fully vaccinated for SARS-CoV-2 (does not include booster vaccination)
- 6) Agree to abstain from any other investigational drug studies for the duration of the study
- 7) Agree to abstain from nasally administered products, including over-the-counter products, for the duration of the study
- 8) Report use of an effective method of contraception at enrollment and intending to continue use of an effective method for the duration of study participation. Acceptable methods include:

a) Males: Male condoms, sterilization of participant or partner, partner use of hormonal contraception or intrauterine device [IUD], identifies as a man who has sex with men exclusively, and/or sexually abstinent for the past 60 days and agrees to remain abstinent for the study duration

b) Females: Hormonal methods at the time of enrollment, IUD inserted prior to enrollment, sterilization of participant or partner, consistent condom use of male partner for at least 28 days (reports using condoms 10 times in the last 10 acts of intercourse), identifies as a woman who has sex with women exclusively, and/or sexually abstinent for the past 60 days and agrees to remain abstinent for the study duration.

NOTE: Male and Female refer to Sex at Birth, not self-identified gender.

Sexually abstinent refers to penile-vaginal intercourse only.

9) Agree to participate in all study-related assessments and procedures

5.5 Exclusion Criteria

Participants who meet any of the following criteria will be excluded from the study:

- 1) Abnormal nasal or throat exam at enrollment
- 2) If female, pregnancy, or within 42 days of last pregnancy at screening
- 3) If female, breastfeeding
- 4) Diagnosed with SARS-CoV-2 in the past 42 days prior to screening
- 5) Diagnosed or suspected respiratory tract infection in the past 14 days prior to screening
- 6) Participation in an investigational drug study in past 30 days at screening
- 7) Any condition that, in the opinion of the Investigator would preclude provision of consent, make participation in the study unsafe, complicate interpretation of study outcome data, or otherwise interfere with achieving the study objectives
- 8) Use of any intranasal product in the 14 days prior to enrollment
- 9) Surgical procedure involving the nose or throat 90 days prior to enrollment
- 10) Any of the following laboratory abnormalities at screening:
 - a.) Hgb < 12g/dL (men) and < 11g/dL (women)
 - b.) Serum creatinine > 1.1 x ULN
 - c.) ALT, AST, and total bilirubin > 1.1 x ULN
- 11) Grade 2 or higher seasonal allergies at the time of enrollment
- 12) Reported use of illicit drugs
 - a. Non-therapeutic injection drug use in the 12 months prior to screening
 - b. Any use of methamphetamine, gamma hydroxybutyrate, cocaine or heroin in the 12 months prior to screening
- 13) Use of systemic prescription immunomodulatory medications within the 4 weeks prior to the enrollment

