Study Regimen:	All participants will apply two metered doses of Q-GRFT in each nostril (400µl total). The spray will be administered by a clinician on the day of enrollment. Participants will be monitored in the clinic for 1 hour after administration and return for a 24-hour post dose visit. If safe and acceptable, a second period of daily administration for 13 days will commence. Safety assessments will be performed at day 7, day 14, and day 28 visits after the initiation of the second period. Additional safety assessments will be done by contacting participants between visit $4 - 5$ and visit $5 - 6$.

Study Schema:

Note: the window between V1 and V2 has been increased to 60 days

Primary Objectives:

• To assess the local and systemic safety of intranasal Q-GRFT after 14 doses **Endpoints**:

• The proportion of participants who experience a related Grade 2 or higher adverse event **Secondary Objectives:**

- Persistence: To determine the persistence of Q-GRFT in the respiratory tract after a single dose and after 13 days of daily use as assessed by nasopharyngeal swab
- Pharmacokinetics: To determine the systemic absorption of Q-GRFT after administration of a single dose and after 13 days of daily use
- Acceptability: To assess the acceptability of a Q-GRFT nasal spray

Secondary Endpoint:

- Persistence: Q-GRFT concentrations from nasopharyngeal swabs collected 24 hours after a single dose and 24 hours after 13 consecutive daily doses
- Pharmacokinetics: Q-GRFT concentrations in plasma 24 hours after the first dose and 24 hours after the 13th consecutive daily dose
- Acceptability: Self-reported assessment of qualities of the experience with the nasal spray through a Likert scoring of acceptability questions

Exploratory Objective:

- To assess the impact of Q-GRFT nasal spray on smell
- Persistence: Q-GRFT concentrations from oropharyngeal and nares swabs collected 24 hours after a single dose and 24 hours after 13 consecutive daily doses
- Presence of Q-GRFT in the gastrointestinal tract after 13 days of consecutive use
- To determine the potential of the Q-GRFT study drug product to induce an immune response by measuring the generation of anti-drug antibodies (ADAs) in plasma/blood samples after multiple Q-GRFT intranasal spray treatments

Exploratory Endpoint:

- Change in Brief Smell Identification Test (BSIT) score after 13 days of consecutive daily doses compared to baseline

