7.3 Visit 2: Enrollment

Subjects who meet the inclusion and exclusion criteria following the Screening visit may schedule an Enrollment visit. This visit is to occur within 60 days of the Screening Visit.

At this visit, locator information will be updated, and eligibility reviewed. Participants will undergo a smell assessment prior to drug delivery. The Brief Smell Identification Test (BSIT) contains 12 odorants embedded on scent strips and released when scratched with a pencil tip. The BIST is a forced choice test as participants are instructed to identify an odorant even if no smell is perceived. The total olfaction score using the BSIT is defined as the number of odorants that are correctly identified.

The participant will be sequence randomized to receive either Q-GRFT nasal spray or placebo nasal spray. The clinician will administer the first dose of study product. After reviewing administration instructions, the participant will try the metered dose delivery system by delivering product into a paper towel. Participants will be asked to wait at the research trial site for one hour after product administration for observation. All participants will undergo an assessment of adverse events, targeted physical exam, blood draw, and assessment of smell approximately one-hour postnasal spray administration.

Interested participants may participate in an optional enrollment visit sampling (nasal, oropharyngeal, and nasopharyngeal) at a single timepoint between 1- and 12-hours post product administration. Participants must agree to all three sample collections to be eligible for this optional enrollment visit sampling.

VISIT 2: ENROLLMENT – PRE		
Component	Procedure/Analysis	
ADMINISTRATIVE	 Review/Confirm Eligibility Collect/Update Contact Information Visit Questionnaire Quality of Life Survey Update Medical History and Concomitant Medications Provide Available Screening Results Protocol Counseling 	
URINE	Pregnancy Test (participants of childbearing potential)	
PHYSICAL EXAM	 Targeted Physical Exam Assessment of Smell (BSIT) Vital Signs (BP) 	
BLOOD	 Q-GRFT level ADA test for Anti Q-GRFT antibodies	
NASAL	Q-GRFT level	
OROPHARYNGEAL	Q-GRFT level	
NASOPHARYNGEAL	Q-GRFT level	
STUDY PRODUCT	 Randomized to study product Study Product Provision Clinician-administered 	
1-HR POST-DOSE		
Component	Procedure/Analysis	
ADMINISTRATIVE	 Assess/Document Adverse Events Schedule Next Study Visit Participant Reimbursement 	

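### The respiratory-infection and SARS-CoV-2 look-backs end at screening, up to 60 days before the first dose, so an infection arising in between meets neither exclusion

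*Combined protocol and SAP*

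**What the plan says.** Two infection exclusions in Section 5.5 count back from screening. Item 4 reads "Diagnosed with SARS-CoV-2 in the past 42 days prior to screening" and item 5 reads "Diagnosed or suspected respiratory tract infection in the past 14 days prior to screening".

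Dosing comes later. Of Visit 2, Section 7.3 says "This visit is to occur within 60 days of the Screening Visit", and at that visit "The clinician will administer the first dose of study product". A note under the Study Schema in the Protocol Summary says that "the window between V1 and V2 has been increased to 60 days".

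Other exclusions in the same list are tied to enrollment: item 1 (nasal and throat exam), item 8 ("Use of any intranasal product in the 14 days prior to enrollment"), item 9 (nose or throat surgery), item 11 (seasonal allergies) and item 13 (immunomodulatory drugs).

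For SARS-CoV-2, the note to inclusion item 4 in Section 5.4 deals with a positive test at the screening visit. If there are no symptoms, "participants may enroll 14 days after a positive test result if they remain asymptomatic". With symptoms, the wait is 14 days from the later of symptom onset or result, and the person must have been without fever for 24 hours. The visit tables list a SARS-CoV-2 test at Visit 1 only; in Table 2 the nasopharyngeal sample is for Q-GRFT level. Section 10.1 nevertheless describes those to be recruited as uninfected with SARS-CoV-2.

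**The concern.** A look-back is meant to keep recent infection away from the period in which outcomes are measured. That period starts at the first dose, not at screening. With a gap of up to 60 days between the two, a criterion that stops at screening can miss the very days that matter.

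The symptoms overlap. Section 10.2 lists congestion, nasal discharge, cough, pharyngitis, altered taste and smell, and headache as possible product effects, and a respiratory infection can cause the same ones. The primary endpoint depends on a clinician judging a Grade 2 or higher event to be related. The smell endpoint (BSIT) is a change from baseline, with the pre-dose test at Visit 2. If smell is reduced at that test and then recovers, a true loss in that participant could be hidden. With 30 and 15 participants, one or two misattributed events are visible in the result.

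**Working it through.** **1. The plan's own figure.** Table 9 gives exact binomial 95% intervals for 30 participants. Two-sided Clopper-Pearson limits reproduce all 16 rows to 0.1 percentage point. For 0/30 the upper limit is 1 − 0.025^(1/30) = 11.6%; for 1/30 it is 17.2% and for 2/30 it is 22.1%. So one infection symptom wrongly judged related in the active arm would move the upper limit from 11.6% to 17.2%, and a second would move it to 22.1%.

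**2. Day counts.** Inputs: 14-day and 42-day look-backs (Section 5.5), 14-day allowance (Section 5.4), gap of at most 60 days (Sections 7.2 and 7.3). Let screening be day 0 and the first dose day g.

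- Days of the 14 before dosing that item 5 does not cover: min(14, g).
- Days of the 42 before dosing that item 4 does not cover: min(42, g).
- Shortest interval to dosing for a respiratory infection before screening: 15 + g.
- Shortest interval for a SARS-CoV-2 diagnosis before screening: 43 + g.
- Shortest interval after a positive test at screening: max(14, g).
- Respiratory infection or SARS-CoV-2 diagnosis after screening: no minimum.

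| g | Uncovered, item 5 | Uncovered, item 4 | Infection before screening | SARS-CoV-2 before screening | Positive at screening |
|---|---|---|---|---|---|
| 1 | 1 | 1 | 16 | 44 | 14 |
| 7 | 7 | 7 | 22 | 50 | 14 |
| 14 | 14 | 14 | 29 | 57 | 14 |
| 30 | 14 | 30 | 45 | 73 | 30 |
| 60 | 14 | 42 | 75 | 103 | 60 |

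**3. A realistic gap.** Sixty days is the maximum. Section 4.6 expects 6 to 8 weeks (42 to 56 days) in total, screening included. On the ideal schedule Visit 2 to Visit 7 takes 1 + (5 to 7) + 28 = 34 to 36 days. That leaves between 42 − 36 = 6 and 56 − 34 = 22 days for the gap. Item 5 then leaves 6 to 14 of the last 14 days uncovered.

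**4. Illustration.** The protocol gives no infection rate. Assume r = 0.5 to 3 respiratory infections per person-year, at a constant rate. The share with an onset in w uncovered days is 1 − exp(−r·w/365.25).

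- w = 14: 1.9% (r = 0.5) to 10.9% (r = 3), or 45 × share = 0.9 to 4.9 participants.
- w = 7: 1.0% to 5.6%, or 0.4 to 2.5 participants.

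These are infections before any safeguard, not endpoint events.

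**The case against.** The plan does not ignore recent illness at Visit 2. Eligibility is reviewed, and medical history and medications are updated before dosing. An abnormal nasal or throat exam excludes, and so does use of an intranasal product in the previous 14 days. Exclusion 7 lets the investigator exclude any condition that would make outcome data hard to interpret. This stands: many people with current symptoms would be noticed. But none of these sets a minimum interval, and a review against criteria worded to end at screening does not make a later infection exclusionary.

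A reader might infer that the primary endpoint is biased. The documents do not support that. An event must be new or a worsening (Section 8.4), reach Grade 2 and be judged related under masking. Randomization spreads such cases over both arms on average. BSIT change is exploratory. What is left is noise and chance imbalance.

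A reader might also infer that the 14-day and 42-day SARS-CoV-2 rules contradict each other. They do not: one covers a positive test at the screening visit, the other a diagnosis before it, and a site can follow both. What remains is unequal stringency. A diagnosis the day before screening excludes the person at that screening, while a positive test at screening permits enrollment 14 days later. No reason is given.

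Finally, 13 of the 14 doses start at Visit 4, at least 5 days after Visit 3. Infections after Visit 2 cause the same symptoms, and no change to the enrollment criteria removes them. That is correct and limits the gain.

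**Conclusion.** The point holds as a gap in two eligibility rules. Any respiratory infection or SARS-CoV-2 diagnosis that arises between screening and Visit 2 falls outside items 4 and 5. From a gap of 14 days on, item 5 covers none of the 14 days before dosing; from 42 days on, item 4 covers none of the 42.

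The consequence is avoidable noise in attributing local adverse events and in the exploratory smell baseline. How much depends on infection rates, the actual gaps and how well the Visit 2 safeguards work, none of which the documents quantify. Under the assumed rates, roughly 0.4 to 4.9 of 45 participants would have an onset in the uncovered days, before safeguards, for uniform gaps of one week and of two weeks or more respectively. No sample size or interval in Section 9.2 changes.

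The SARS-CoV-2 rules are a separate, smaller matter: unequal, unexplained, and silent on infection after screening.

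**What to change.** **Item 5.** Count the existing look-back from enrollment instead of screening, as items 1, 8, 9, 11 and 13 already do, and ask about it again at the Visit 2 eligibility review. State whether SARS-CoV-2 counts as a respiratory infection under this item. Otherwise a person enrolling exactly 14 days after a positive screening test could be allowed by inclusion item 4 and excluded by item 5.

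**SARS-CoV-2.** The sponsor should reconcile inclusion item 4 (Section 5.4), exclusion item 4 (Section 5.5) and the description of the population in Section 10.1, give the reason for any difference in stringency, and state which rule applies to infections arising after screening. Simply moving the 42-day rule to enrollment would not do, because it would then contradict the allowance in inclusion item 4. No interval is proposed here.

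**Cost.** A wording amendment and a repeat question at a review that already takes place. A few participants would be delayed or rescreened.

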6 STUDY PRODUCTS

6.1 Regimen

Each participant will receive a total of 14 doses of intranasal Q-GRFT. A dose consists of two sprays into each naris (400 μ L total).

6.2 Administration

To ensure appropriate placement, the clinician will administer the study product for the first application. Participants will be instructed on the proper use of the applicator and have an opportunity to practice spraying into a paper towel. Thereafter, participants will administer the product themselves.

6.3 Study Product Formulation

Griffithsin (GRFT) is a non-glycosylated protein consisting of 121 amino acids. The API to be used in this trial contains a single amino acid substitution, M78Q variant, that is resistant to oxidation yet maintains the parent molecule's pharmacological profile⁶. The drug product is a mixture of Q-GRFT API and excipients at a final concentration of 7.5 mg/mL. The Q-GRFT API used for drug product manufacture is available as a suspension in PBS at 10±2 mg/mL. The final drug product is filled into metered pump nasal spray applicator, Aptar VP7 screw-on actuator fitted to an SGD Type 1 Glass Amber U-Save bottle (fill volume not less than 5.5 mL), for intranasal administration. A matched vehicle solution is also manufactured and dispensed in same applicators. The device requires 5 sprays for priming before first time use and no priming required thereafter for subsequent administrations. Both placebo and DP should be stored at 2-8°C. The placebo and drug product are manufactured in the [name] Pharmaceutics Laboratories with CBR International serving as the Quality Assurance as per the regulatory requirements for phase 1 products. Additional details regarding study product may be found in the study specific pharmacy manual.

6.4 Study Product Supply and Accountability

cGMP Q-GRFT and placebo nasal spray bottles will be sent to the Magee-Womens Hospital Investigational Pharmacy, and stored at 2-8°C.

The Magee research pharmacist will maintain complete accountability records of all study products received for this protocol and provided to participants. Additional documentation will be required for study product returns, destruction (if applicable). Unused (once dispensed) study products will be handled according to the study specific pharmacy manual.

6.5 Study Product Provision

Study product will be provided to clinic staff only upon receipt of a written prescription signed by an authorized prescriber. Once the nasal spray bottles are dispensed from the pharmacy and provided to the participant, the bottles can be stored at room temperature.

6.6 Concomitant Medications

Enrolled study participants may use concomitant medications during study participation except immunomodulating drugs and intranasal products as detailed below. All concomitant medications, over-the-counter preparations, vitamins and nutritional supplements, recreational drugs, and herbal preparations will be recorded on the concomitant medications log form.

All participants will be counseled to avoid the use of intranasal products. Prohibited non-study intranasal products include, but are not limited to, decongestants, saline, steroid, and antihistamine sprays. Participant use of prohibited medications will be documented.

